feedback. *Stepping Together*, written on a 6th grade level, provides a step-by-step approach for parents to provide treatment at-home with 11 parent-child meetings. Weekly phone support is provided for support, coaching and motivation. Pilot data suggest that ~89% of scheduled phone calls occurred. When calls did not occur, the therapist or parent would leave a message confirming the next time available to talk. There is also a *Stepping Together* website with two video demonstrations (see Appendix). Step Two is therapist-led and consists of 9 weekly (90 minute) TF-CBT therapy sessions [62, 63](see c.3.1.).

After completing Step One, a brief assessment occurs. If responder status is met, the parent and child end treatment and proceed to the Maintenance phase which is designed to further open parent-child communication and encourage the parent and child to use the tools that they learned in Step One. Responder status criteria was developed and tested in the pilot studies.[7] Establishing responder status involves three methods of measuring treatment response/nonresponse: 1) a semi-structured interview (with parents for young children ages 4-6 and with parents and children for children ages 7-12) about PTSD symptoms. Responders must have 3 or fewer symptoms for younger children and 4 or fewer symptoms for older children. The one symptom difference is based on prior research on PTSD with young children that documented that fewer symptoms are needed for young children to meet criteria[64] and recent differences in number of symptoms needed for PTSD diagnosis based on age according to DSM-V[65]; or 2) below the clinical cut off score on a continuous measure of PTSD symptom severity (completed by parents for young children and by the child for older children); and 3) a rating of 3 (improved), 2 (much improved), or 1 (free of symptoms) on the Clinical Global Impression–Improvement scale (CGI-I)[66] that takes into account impairment. Results from our pilot data on SC-TF-CBT suggest even before responder status is determined, there are two additional second-stage tailoring variables (e.g., non-compliance and concurrent trauma exposure) that should indicate a “trigger and switch” approach to an immediate step-up to Step Two (see c.1.3.).

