change in HR and SC responses to the interview relative to baseline. 2) A subjective unit of distress (SUD) scale which is commonly used will be rated by the child using a developmentally appropriate SUD rating (i.e., “scary feeling score,” 0-3 or 4). Prior research with young children as well as our experience suggests that children age 4 and older understand the rating scale and can provide these data. Similar to our pilot work, children will provide six ratings during exposure or trauma-related activities and parents will record these ratings. In TF-CBT, the child ratings will be recorded by the therapist. The first rating will occur before the exposure/activity, four during the activity with the highest being recorded as the peak rating and one after the exposure/activity. Changes in trauma-related negative appraisals: The *Post-Traumatic Cognitions Inventory-child version (CPTCI)*, is a 25-item child report of negative trauma-related cognitions. The CPTCI has demonstrated excellent psychometrics and no age-related differences in scores for children ages 6-18. The measure will be administered with children ages 6 to 12 (~78% of the sample). Expectancy of negative outcomes (ENOs): The ENOs measure, modified from [name] et al. and similar to Deacon et al., is a 3-item parent report of the child’s perceived expectancy of a negative outcome that is rated (0 to 100) before and after the trauma-related activity. Children’s fear toleration (CFT): Similar to Deacon et al., parents will rate (0-100) the extent of the child’s fear toleration when participating in the trauma-focused activity. Therapeutic worry and alliance will also be examined as potential mechanisms of change which will be measured using the treatment worry questionnaire at baseline only (child and parent version) and the Therapeutic Alliance Scale for Children (TASC, parent, child, and therapist version) administered the same assessment time periods as the HR and SC (i.e., Weeks, 0, 2,4 = Step One & 0,5,8= TF-CBT and at post-assessment) (Keeley et al. 2011). As indicated in Table 1, the mechanism of change measures will occur at post-assessment too. The “trauma-related activity” will be a 5 minute semi-structured interview that consists of the same guide that is used during the HR and SK test. After these measures are completed the parent and child will be asked independently 6 questions about their experiences talking about what happened, including how they may have changed. These responses will be used to triangulate the quantitative measures.

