**Within session ratings.** Parents will rate fear toleration and negative expectancy after each trauma-related activity in therapy sessions and parent-child meetings. As in previous NIH-funded clinical trials (PI: [name], study therapist [name], R34MH070827-01A1; 1RC1MH-088969-01), therapist-directed sessions will be video taped. We will systematically identify the child’s participation in the trauma-focused activity within each session and have parents review that segment via video (~15 min.) during the beginning of the time when the parent meets with the therapist. These research procedures will not significantly influence treatment outcome as discussing with the parent what the child completed in therapist-led sessions is current protocol for both treatments, and similar procedures have been used in previous trauma-focused clinical trials with children 3-12. This procedure allows the parent to have direct observation of the child and allows the parent time to process the observations with the therapist. Viewing video segments will not be needed when there are conjoint sessions. For the at-home parent-child meetings, the parent will complete the ratings immediately after the meetings. Children will complete the *CPTCI* at the beginning of Weeks, 0, 2,4 in Step One & 0,5,8 in TF-CBT and the SUDS rating during treatment. For Step One, measures will be in the parent’s *Stepping Together* book, and therapists will collect these measures at each meeting and will remind parents about the measures during the phone meetings. Since Step One and TF-CBT occur within different timeframes (6wks vs. 3mo), the physiological measures will be administered based on when components are covered and during scheduled in-office visits for Step One patients: at session 1, after the coping skills components, and after four exposures in Step One or the trauma narrative in TF-CBT (Table 1). The frequency of four potential mechanism of change measures (e.g., fear based arousal measure (subjective unit of distress), trauma-related negative appraisals, expectancy of negative outcomes, and fear toleration) will be 12 for both conditions. Step One patients will not complete these measures during parent-child meetings 1 and 2 as these meeting occur directly after the first therapist meeting.

**c.6.7. Fidelity Measures.** All of the fidelity measures were successfully utilized in the pilot trials of SC-TF-CBT.

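### The ENOs measure is defined as rated before and after the trauma activity, but c.6.6 collects it only afterwards and gives no way to obtain the 'before' score

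*Combined protocol and SAP*

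**What the plan says.** Section c.6.5 introduces ENOs as a three-item parent report of the child's "expectancy of a negative outcome that is rated (0 to 100) before and after the trauma-related activity". So the definition calls for two ratings per activity.

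Section c.6.6, under Within session ratings, is the only place that explains how these ratings are collected during treatment. It states: "Parents will rate fear toleration and negative expectancy after each trauma-related activity in therapy sessions and parent-child meetings". It then separates the settings:

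- In therapist-directed sessions, staff identify the child's trauma-focused activity on the recording and "have parents review that segment via video (~15 min.) during the beginning of the time when the parent meets with the therapist".
- Conjoint sessions are the exception, because the parent is in the room and no recording has to be shown.
- Step One meetings at home have a rule of their own: "the parent will complete the ratings immediately after the meetings".

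The same section says that the number of mechanism ratings "will be 12 for both conditions". Table 1 adds only that ENOs is taken at every session or parent-child meeting and at post-assessment. It does not place the rating relative to the activity.

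Two analysis texts use the mechanism measures: c.8.3 (Primary Aim 3) and the Amendment to the analysis plan 2.11.2022. The amendment replaces latent difference score models with mixed models for change over time, and tests whether the rate of change differs between standard TF-CBT and Step One responders. Neither text says which ENOs score is modelled: the before score, the after score or their difference.

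**The concern.** A rating of what the child expected has its intended meaning only if it is given before the outcome is known. Once the parent has watched or led the activity, a 'before' score is a recollection and may drift towards what happened.

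This touches a stated hypothesis. Section b.2 treats change in negative expectancy as a primary mechanism of inhibitory learning, and Hypothesis 3.1 includes decreases in it among the mediators. Section c.6.6 also sets out to show that mediators changed before outcomes, so the time at which a mediator is rated is part of the argument.

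A second issue is that the rater's position is not the same in the two groups that Aim 3 compares. A Step One parent mostly rates a meeting that he or she has just led. A standard TF-CBT parent mostly rates from a recording. Treatment and rating mode are therefore entangled in any between-group comparison of ENOs.

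**Working it through.** **Step 1. Reproduce the plan's own count.** Inputs: 11 at-home meetings (b.2, "parents to provide treatment at-home with 11 parent-child meetings"); no mechanism ratings at meetings 1 and 2 (c.6.6); 3 Step One therapist meetings (b.2, c.3.1); 12 standard TF-CBT sessions (c.3.1).

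- Step One: 3 + (11 − 2) = 3 + 9 = 12.
- Standard TF-CBT: 12.

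Both agree with the stated 12.

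**Step 2. Split the occasions by setting.**

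| | At home, parent-led, rated straight after the meeting | Therapist session, rated after video unless conjoint |
|---|---|---|
| Step One | 9 of 12 (75%) | 3 of 12 (25%) |
| Standard TF-CBT | 0 of 12 | 12 of 12 |

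The number of conjoint sessions is not given, so the share rated from video in standard TF-CBT cannot be fixed.

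**Step 3. Look for a 'before' step in each setting.** At home, the ratings follow the meeting. In non-conjoint therapist sessions, they follow a video of a finished activity. In conjoint sessions the parent is present, but the general rule in c.6.6 still puts the rating after the activity. No setting has a prospective rating.

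**Step 4. Compare with measures whose early rating is spelled out.** For the SUD scale, c.6.5 puts the first of six ratings before the activity and says who records it. For TSCYC-PTS and CSDS-P, c.6.6 specifies the start of each session or parent-child meeting. For the CPTCI, c.6.6 specifies the beginning of the scheduled weeks. ENOs is the measure with a 'before' part in its definition and no matching step in the procedure.

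**Step 5. What a hindsight score would do.** Let B be the true prior expectancy, A the after-rating, and h the assumed fraction by which hindsight pulls the recorded 'before' score towards A.

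- Recorded before score: B* = B − h(B − A).
- Recorded within-activity change: B* − A = (1 − h)(B − A), an understatement by the fraction h.
- After score: A, which does not depend on h.

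The documents give no value for h, so any percentage obtained this way merely restates the assumption. If h differs between groups or changes across sessions, group trajectories of B* or of B* − A could differ with no true difference. The documents give no information on either possibility.

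**The case against.** The strongest reply is that c.6.5 requires a 'before' rating explicitly, and silence in c.6.6 should not override it. Nothing in the documents says that the score is filled in retrospectively. Parents already complete forms at the start of each session or meeting, and the Step One measures are in a workbook whose layout is not shown. This stands against one inference that a reader might draw, that expectancy is never measured prospectively. The post-assessment rating is also separate: it concerns a 5-minute interview, and neither the video procedure nor the home-meeting procedure is stated to apply there. The reply does not remove the contradiction. The start-of-session contact is assigned only to TSCYC-PTS and CSDS-P, and c.6.6 gives ENOs a time of its own.

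A reader might also infer that the whole inhibitory-learning test fails. It does not. Fear toleration, the other inhibitory-learning measure, concerns the child's behaviour during the activity, so rating it afterwards is appropriate.

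A third inference would be that the Aim 3 comparison is shown to be biased. The documents do not support that. The video is meant to give the parent direct observation and may cover the whole activity, and 3 of the 12 Step One occasions are therapist sessions too. The amended Aim 3 examines change over time, and no text says that the within-activity difference is analysed. If the after-rating is the modelled score, hindsight in the 'before' item does not enter.

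**Conclusion.** The contradiction between c.6.5 and c.6.6 on ENOs timing is established from the text. Under c.6.6 as written, it covers all 12 within-treatment occasions in each condition, and any 'before' score there would be retrospective. Rating mode differs between the conditions (9 of 12 occasions at home in Step One, none in standard TF-CBT), so the amended comparison of rates of change in expectancy may be affected.

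Three things remain open: whether sites actually collected the item in hindsight, which ENOs score was modelled, and how large any distortion is and in which direction. None can be settled from the documents. The point concerns one of the four hypothesised mediators in Aim 3. It does not touch fear toleration, the post-assessment rating or the Aim 1 non-inferiority result. It should be corrected, but it does not threaten the trial's main conclusion.

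**What to change.** 1. Amend c.6.6 so that the three ENOs 'before' items are completed before the activity. Put them with the TSCYC-PTS/CSDS-P form at the beginning of each session or parent-child meeting and, for home meetings, on the workbook page preceding the activity. Keep the 'after' items and fear toleration after the activity or video.
2. State in the Aim 3 plan which ENOs score enters the models: before, after or change.
3. The 2022 amendment reports its analyses in the past tense, so for data already collected, check the forms to see when the 'before' items were completed in each setting and disclose the answer. Where they were completed retrospectively, base the expectancy analysis on the trajectory of after-ratings only. Do not set aside 'before' data without making this check. Report the difference in rating mode between the conditions as a limitation, since after-ratings share it.

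The collection change moves three items and adds to a workbook page, with no extra visit. One limit remains: in non-conjoint sessions, a parent rating at the start reports the child's expectancy about an activity that the parent has not yet seen. The form wording should allow for that. For data already collected, the cost is a review of the forms and a sentence or two of disclosure.

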### **c.8. Data Analysis**

**c.8.1. Overview.** As in the R34 study, [name] will design a customized web-based randomization, data entry and management system for this project. We will use Qualtrics, a widely used secure web-based software package to collect data. Therapist will also use Excel to enter de-identified fidelity and cost data. Data will be uploaded to Box. (see Protection of Human Subjects 5.1.1.a.). [name] will work closely with the PI on the development of the data management system and with the PI/ Co-Is in the data management/analysis of the psychological, physiological and cost-related data.

**c.8.2. General Analytic Plan.** Descriptive and graphical statistics will be used to summarize the data on all randomized patients and to confirm that there are no group or site differences ( $p < .10$ ) in baseline demographics and clinical characteristics. If, for example, site differences are detected, we will account for it by including site indicators as fixed effects in the model. Distributional assumptions will be checked and appropriate transformations or non-parametric methods will be applied as necessary. For Primary Aim 1, we will use methods that are based upon establishing equivalence or non-inferiority of outcomes across treatment arms. These methods are used classically to evaluate whether a new treatment or condition is not inferior to an existing treatment. In general, Generalized Linear Models (GLM) will be used throughout. These models account for deviation from normal assumption of the dependent variables and to control for baseline covariates including patients' demographics and corresponding child and parents assessment measures. For Primary Aim 2, GLM will be used to quantify the relation between the value of the tailoring variables and the propensity of not responding to Step One. For Primary Aim 3, latent difference score models (LDS) will be applied. We will mainly use SAS 9.3 and Mplus 7.1 for GLM and mediation analysis. For Primary Aim 4, a cost effectiveness analysis (CEA) will be performed. CEA measures the incremental cost per unit improvement in outcomes. In the absence of outcome differences, costs will be examined using GLM.

### **c.8.3. Specific Analyses for the Individual Study Aims**

**Primary Aim 1:** For the primary and secondary hypotheses, one-sided tests for non-inferiority will be applied as our goal is to show that the performance of the children in SC-TF-CBT will demonstrate comparable improvements to children in standard TF-CBT. For this non-inferiority test, the null hypothesis is written as  $H_0: \mu_1 - \mu_2 > r^*$ , where  $\mu_1$  denotes the average improvement in standard TF-CBT and  $\mu_2$  denotes the average improvement among children in SC-TF-CBT, and  $r^*$  represents the clinically significant difference expressed as common standard deviation units. The test will be applied to child outcomes, acceptability/satisfaction levels and parent outcomes that will be measured at post-treatment and at 6- and 12-month follow-up respectively.

Rejection of the null hypothesis will indicate that treatment outcomes of SC-TF-CBT are comparable to those from standard TF-CBT. For child and parent outcomes only, we will further apply GLM with repeated measures to detect whether the two treatment groups perform differently at any one time point. We will also document the percentage of responders to Step One and numbers and reasons for trigger and switch.

**Primary Aim 2:** To examine tailoring variables that could be used to individualize the decision of which children should be assigned at baseline to SC-TF-CBT versus standard TF-CBT, we will compare the responders/non-responders of Step One with regard to the value of the tailoring variables. Based on results from pilot studies, we hypothesized that children with more internalizing problems at baseline and those from families with potential life event barriers are less suitable for SC-TF-CBT. A Chi Square test will be first applied to evaluate the association between the dichotomized candidate tailoring variable and responding status. Next, we will use GLM, in which responding status will be treated as the dependent variable and tailoring variables as continuous predictors. To further quantify the relation between the value of the tailoring variables and the propensity of not responding to Step One, we will include in the GLM the products of the tailoring variables to evaluate their interactions. Demographics will also be controlled in the model. While it was not a primary aim, we will further explore whether race/ethnicity or gender moderate the dropout rate and treatment outcomes (see 6.). This will be done in a separate analysis where interactions with treatment condition are included.

**Primary Aim 3:** We will examine four potential mechanisms of change on both Step One and TF-CBT including fear arousal, maladaptive cognitions, expectancy of negative outcomes, and fear toleration. The analysis of mechanism of change will have two phases. First, we will run univariate latent difference score (Goldstein, #1) models on the longitudinal observations of potential mediator and outcome variables. Since the fear-arousal variables (HR and SC) that both assess sympathetic nervous system activation are typically correlated, and combining physiological responses into single indices is common (e.g.,), we will attempt to combine them into a single index. LDS incorporates features of latent growth curve modeling and cross-lagged regression models and is appropriate in research on mechanisms of change. We will compare univariate LDS models for time invariant and time-varying proportional coefficients as well as a no change score LDS model to find the model that best depicts the mechanism. The model selection process will run independently across all potential mediators and outcome variables. Second, we will run bivariate LDS by pairing between two univariate LDS models that have been identified. These pairings include mediator-mediator, mediator-outcome, and outcome-outcome types. We will identify coupling pattern by comparing three candidate models (within the bivariate LDS models): no coupling between the two series, unidirectional coupling in which the change in one variable leads to the other, and bidirectional coupling or cross lagged pattern. For the secondary hypothesis 3.2., we will add a time varying qualitative indicator for direct exposure activities and its interaction with the change component. A significant interaction term indicates the mechanisms are different for the more direct (i.e., Step One) and less direct exposure activities (i.e., TF-CBT). We will also use open coding methods to capture a range of categories related to children and parents experience of talking about the trauma narrative (a trauma related activity used during the mechanism of change measures) and changes that may have occurred during treatment. Thematic content analysis (Patton, 2002; Corbin & Strauss, 2008) will be used to establish the range of participants' experiences and changes.

**Primary Aim 4:** CEA examines the relative value of SC-TF-CBT (versus standard TF-CBT). CEA is performed from a societal perspective, meaning the costs to the health care system and the patient/parents are included. Treatment costs include direct (e.g., cost of therapy session), indirect (e.g., travel costs, missed work), and opportunity costs (e.g., value of lost time; see c.1.5. & c.7.4. for cost measures). CEA often incorrectly omits the opportunity cost of patient/parent time spent on therapy, phone support, and at-home parent-child meetings. Non-study mental health service costs include inpatient, outpatient, and school-based services and will be priced using the Florida Medicaid fee schedule. Research-specific costs (e.g., screening, research consent) for patients and staff are excluded. GLM will be used to examine differential treatment costs for SC-TF-CBT and standard TF-CBT. GLM can account for the likely skewed distribution of costs, differences in child characteristics, and a potential lack of independence within treatment locations. Incremental cost effectiveness ratios (ICER) are computed as incremental costs divided by incremental changes in morbidity/outcomes (symptom reduction and change in impairment/functioning). A single outcome measure (e.g., Quality Adjusted Life Years) might be preferable, but no established parameters for estimating morbidity in young children with trauma exist. If outcomes differ significantly, a non-parametric bootstrap with replacement method is used to generate a joint distribution of differential costs and outcomes. If outcomes do not differ, cost-effectiveness is determined by comparing treatment costs. Mean and median ICER ratios are reported as well as 95% confidence

intervals. Cost-effectiveness acceptability curves examine the probability of falling below a variety of cost-effectiveness thresholds. In addition to the ICER approach, the net-benefit approach will be used to determine if findings are sensitive to method. If tailoring variables effectively distinguish children who respond to Step One, CEA will also be performed for children with low scores on tailoring variables. CEA will not be performed for children with high scores on the tailoring variables since the preliminary data indicate that standard TF-CBT is necessary for these children (c.1.2.). Race/ethnicity and gender differences in CEA will be assessed if treatment outcomes vary (see 6. Inclusion of Women and Minorities).

**c.9. Sample Size Considerations and Power Analyses.** We will enroll a total of N=216 subjects with a 1:1 randomization between SC-TF-CBT and standard TF-CBT. Based on our successful track record in obtaining post and follow-up data in our R34 SC-TF-CBT trial (only 3.77% missing post- data, and 6.1% missing 3-mo. follow-up data, N=53), and the PIs previous child trauma clinical trial with a 1-year follow-up (8.57% attrition), we conservatively anticipate 15% attrition at post-assessment resulting in 184 subjects (92 per group) and a 10% lost to follow-up at 6- and 12-months resulting in 166 subjects (83 per group) and 150 subjects (75 per group), respectively. Sample size requirement was determined by CEA for Primary Aim 4 and it also provides sufficient power for Primary Aims 1 to 3 under various assumptions. **Primary Aim 1**, Hypothesis 1.1, the study will have 80% power to show that SC-TF-CBT is at least as effective as standard TF-CBT. This assumes an alpha of .05, sample size of 92 per group after attrition and a difference of 0.41 SD units or less as unimportant. We expect to maintain the same power of 80% in testing the hypothesis (1.2.) that focuses on the outcomes at follow-up (6- and 12-months). Though we may lose an additional 10% of participants at each follow-up point, reduction in measurement error through repeated measures and use of multiple imputation method will mitigate the sample size loss. For **Primary Aim 2**, 80% power will be achieved for detecting responding rates difference between 62% and 30%, 72% and 40%, or 80% and 50%. This assumes that we divide the patients into two equal size groups based on the tailoring variable value with a total of 92 patients (SC-TF-CBT condition only). For **Primary Aim 3**, we will have >80% power to detect a small to moderate effect (0.29) in a unidirectional bivariate latent different score model with complete longitudinal observation for the 184 children under both conditions (for analyses involving CPTCI, the detectable effect size is 0.33). For the secondary hypothesis 3.2., we have moderate power (.57) to detect different strengths of the unidirectional prediction between the two conditions (e.g., 0.15 vs 0.45 or .00 vs .30; for the CPTCI, the power for the same comparisons is .55). For **Primary Aim 4**, the study will have 80% power to detect cost differences between SC-TF-CBT and standard TF-CBT, assuming medium effect size (.5), an alpha of .05 and sample size of 92 per group. The sample size will also be sufficient to maintain 80% power to detect a medium effect size for children with low values for the tailoring variable, and to detect a large effect size for children with high values.

**c.10. Attrition and Missing Data.** Overall retention rate at each data point is expected to fall within the acceptable range, with percentages of missing data well within acceptable ranges for statistical correction (10 to 15%). The IE will be alerted via Qualtrics™ if any items are missing during assessment and any paper-and-pencil measures will be visually screened for any missing items. Participants will be asked if they want to complete any unanswered items. Every effort will be made to prevent dropouts/missing data, and to complete relevant assessments for patients who drop out or are withdrawn, including reasons why treatment was ended. As is typical in longitudinal research, we must anticipate non-random missing data. We plan to use multiple imputation methods developed by Schafer.

